3.1 INCLUSION/EXCLUSION CRITERIA

The investigator or his/her designee must ensure that all patients who meet the following inclusion and exclusion criteria are offered enrollment in the study.

3.1.1 Inclusion criteria

- 1. Male or female patients ≥ 18 years.
- 2. Patients with clinically non-functioning pituitary macroadenomas ≥ 1 cm.
- 3. No previous treatment for NFPA.
- 4. Eastern Cooperative Oncology Group (ECOG) performance status 0 or 1.
- 5. Written informed consent obtained prior to any screening procedures.

3.1.2 Exclusion criteria

- 1. Patients who require a surgical intervention for relief of any sign or symptom associated with tumor compression.
- 2. Previous pituitary surgery.
- 3. Previous medical treatment for pituitary tumor.
- 4. Patients who have received pituitary irradiation within 10 years prior to inclusion visit (Visit 2).
- 5. Prolactin (PRL) levels > 100 ng/mL. (PRL evaluation should be performed with diluted samples to make sure to avoid the "hook effect.").
- 6. Patients with compression of the optic chiasm causing acute clinically significant visual field defects.
- 7. Diabetic patients whose blood glucose is poorly controlled as evidenced by HbA1C >8%. Diabetic patients whose blood glucose is poorly controlled as evidenced by HbA1C >8%. Patients with a known history of impaired fasting glucose or diabetes mellitus with HbA1c <8% may be included; however, blood glucose and anti diabetic treatment must be monitored closely throughout the trial and adjusted as necessary.
- 8. Patients with known disease of the bile duct or gallbladder, acute or chronic pancreatitis (patients with asymptomatic cholelithiasis and asymptomatic dilatation of the bile duct may be included).
- Patients with abnormal coagulation (PT and/or APTT elevated by 30% above normal limits) or patients receiving anticoagulants that affect PT (prothrombin time) or APTT (activated partial thromboplastin time).
- 10. Patients who have congestive heart failure (NYHA Class III or IV), unstable angina, sustained ventricular tachycardia, ventricular fibrillation, advanced heart block or a history of acute myocardial infarction within the 24 weeks preceding enrolment visit (Visit 2).

- 11. Screening (Visit 1) or baseline (predose, Visit 2) QTcF > 450 msec.
- 12. History of syncope or family history of idiopathic sudden death.
- 13. Sustained or clinically significant cardiac arrhythmias.
- 14. Risk factors for Torsades de Pointes such as uncorrected hypokalemia, uncorrected hypomagnesemia, cardiac failure, clinically significant/symptomatic bradycardia or high grade AV block.
- 15. Concomitant disease(s) that could prolong the QT interval such as autonomic neuropathy (caused by diabetes or Parkinson's disease), HIV, cirrhosis, uncontrolled hypothyroidism or cardiac failure.
- 16. Patients who are taking medication(s) known to increase the QT interval.
- 17. Patients with liver disease such as cirrhosis, chronic active B or C hepatitis or chronic persistent hepatitis, or patients with ALT and/or AST more than 2 x ULN, serum bilirubin > 1.5 ULN, serum albumin < 0.67 x LLN.
- 18. Patients with serum creatinine > 2.0 x ULN
- 19. Patients with WBC $< 3 \times 10^9 / L$; Hgb < 90% LLN; PLT $< 100 \times 10^9 / L$.
- 20. Patients with any current or prior medical condition that, in the judgment of the investigator may interfere with the conduct of the study or the evaluation of the study results.
- 21. History of immunocompromise, including a positive HIV test result (ELISA and Western blot). A HIV test will not be required; however, previous medical history will be reviewed.
- 22. Known hypersensitivity to somatostatin analogues or any other component of the pasireotide LAR.
- 23. Patients with active malignant disease within the last five years (with the exception of basal cell carcinoma or carcinoma in situ of the cervix)
- 24. Patients with the presence of active or suspected acute or chronic uncontrolled infection
- 25. Female patients who are pregnant or lactating, or are of childbearing potential and not practicing a medically acceptable method of birth control. If a woman is participating in the trial then one form of contraception is sufficient (pill or diaphragm) and the partner should use a condom. If oral contraception is used in addition to condoms, the patient must have been practicing this method for at least two months prior to the enrollment and must agree to continue the oral contraceptive throughout the course of the study and for 3 months after the study has ended. Male patients who are sexually active are required to use condoms during the study and for three month afterwards as a precautionary measure (available data do not suggest any increased reproductive risk with the study drugs)
- 26. Participants in investigational drug study 30 days before enrolment visit (Visit 2). Patients must have recovered from all side effects of other investigational therapy.
- 27. History of non-compliance to medical regimens, or patient who is considered potentially unreliable, or any circumstance at the time of study inclusion that would preclude completion of the entire study or the required follow up .
- 28. Patients who have a history of alcohol or drug abuse in the 12 month period prior to Visit 1 (Screening).
- 29. Presence of the surface antigen of hepatitis B (HBsAg).
- 30. Presence of the antibody test for hepatitis C virus (anti- HCV).
- 31. Patients who have undergone major surgery/surgical therapy for any cause within 4 weeks prior to randomization.
- 32. Patients with confirmed hypothyroidism, hypoadrenalism, and hypogonadism (except physiologic menopause and andropause), unless they are adequately treated with stable doses of hormone replacement therapy for a minimum of 3 months prior to study entry .
- 33. Patients in use of growth hormone replacement .
- 34. Uncontrolled cardiovascular, kidney, or metabolic disorders.
- 35. Serious neurologic or psychiatric disorders.

36. Contraindication to MRI such as (but not limited to): cerebral aneurysm clips, cardiac pacemaker, retained cardiac pacemaker wire and temporary pacemaker, cochlear implants, hearing aids that contain internal and non-removable parts, Swan-Ganz catheter, aortic balloon, aortic prosthesis type Zenith AAA Endovascular Graft, other possible contraindications related to ferromagnetic material identified in the patient interview.

4 Visit schedule and assessments

Table A 1 and **Table A 2** list all of the assessments for the Core Phase and Extension Phase, respectively, and indicates with an "X" the visits when they will be performed. All data obtained from these assessments must be supported in the patient's source documentation. The table indicates which data are entered into the database (D) or remain in source documents only (S). Assessments that generate data for database entry and which are recorded on eCRFs are listed using the eCRF name.

Table A 1: Visit Schedule and Assessments for Core Study

Visit number	1	2	3	4	V401 ^E 48	5	6	7	8	9	10 TDE ³	11 FU Visit
Days¹	Day -28 to - 1	Day 0	Day 20	Day 28	Day 48	Day 56	Day 76	Day 84	Day 112	Day 140	Day 168	Day 196
Week of treatment		Enrolment	Week 3	Week 4	Week 7	Week 8	Week 11	Week 12	Week 16	Week 20	Week 24	Week28
	Screening ²	Baseline/ Injection 1	Safety only	Injection 2	Safety only	Injection 3	Safety only	Injection 4	Injection 5	Injection 6	Injection 7# (if patient will join the Extension Phase)	Safety FU
Informed consent (S)	Х											
Demography (D)	х											
Diagnosis and extent of disease (D)	х											
Relevant medical history/ current medical conditions (D)	Х											
Inclusion/exclusion criteria check (S)	х											
Vital signs (D)	Х	Х	Х	Х	Х	Х	Х	Х	Х	х	Х	Х
Physical exam (S)	Х	х	Х	Х	Х	Х	Х	Х	Х	Х	Х	Х

Height (D)	х											
Weight (D)	х	х	Х	х	Х	х	Х	х	х	х	Х	Х
Symptom assessment/ Disease-related symptoms ⁴ (D)	х	х	Х	х	Х	х	Х	Х	х	х	Х	
ECOG performance status (D)	х	х	Х	х		х	Х	Х	х	х	Х	Х
ECG ¹⁴ (D)	х	х	Х	х		х	Х	х	х	Х	Х	
Serum pregnancy test 5,6	х							х			Х	
Hematology (BD)	х			х		х		х	х	х	Х	
Coagulation parameter PT (D)	х	Х	X ¹⁴	X ¹⁴	X ¹⁴	X ¹⁴	х				Х	
Coagulation parameter APTT (D)	х	Х					х				Х	
Urinalysis ⁶ (D)	х			x		х		х	x	х	Х	
Fasting Blood Glucose, Insulin ⁶	х			x		х		х	x	х	х	
HbA1c ⁶	х							х			Х	
Biochemistry ^{6,8} (D)	Х			х		х		х	Х	х	Х	
LFTs (ALT, AST, total bilirubin, albumin, ALP, γ-GT) (D)	х	х	X ¹⁴	X ¹⁴	X ¹⁴	X ¹⁴	Х				Х	
Hbs-Ag and anit-HCV (D)	Х											

Vitamin B12, folic acid ⁶	х										Х	
Hormonal evaluation ^{6,9} (D)	х			х				х			Х	
Alpha subunit evaluation ⁶	Х			х				Х			Х	
Visual field (camp) evaluation 10 (D)	х	X ¹⁰		х		х		х	x	х	Х	
Gallbladder ultrasound (D) 15	Х										Х	
Pituitary MRI / Sella turcica ¹⁵	Х			х				Х			Х	
Adverse events (D)		Х	Х	х	Х	х	Х	Х	х	х	Х	
Pasireotide LAR administration (D)		х		х		х		Х	x	х	X#	
Prior/Concomitant medications ¹¹ (D)	х	х	Х	х	Х	х	Х	Х	Х	х	Х	
Study completion ¹³ (D)												X ¹³

Pasireotide dose on this visit will be administered to selected patients, as per physician discretion, if the patient will be included in the Extension Phase based on response assessed by investigator/ benefit with the drug.

 $^{^{1}}$ Will be allowed a window of \pm 3 days for the planned visits and assessments, unless otherwise specified.

 $^{^{2}}$ It will be allowed a window of \pm 3 days for the planned visits and assessments, unless indicated otherwise.

³ To be completed prior to study drug administration

⁴ To be completed if the patient discontinues prematurely or at study completion.

⁵ Disease related symptoms that will be evaluated: headache, visual disturbances, fatigue, decreased libido, erectile dysfunction (for males only), irregular or stopped menses (for not post-menopausal female only). The investigator will also ask the patient to score the symptoms according to a five-point score scale (0=absent, 1=mild, 2=moderate, 3=severe, 4=very severe). The others will be assessed as present or absent.

- ¹⁰ Hormonal evaluation (serum)—pituitary disease assessments: testosterone (for male), estradiol (for female), prolactin, free T4, TSH, LH, FSH, GH, IGF-I, cortisol, ACTH, asubunit. If the evaluation of the visual field in the selection is performed within 14 days prior to Visit 2, it can be considered as the baseline and there is no need to repeat it for Visit 2.
- ¹¹ Assess with standard automated perimetry (SAP). It is suggested Humphrey Field Analyzer. The window to perform SAP should be no more than 7 days before the scheduled visit.
- ¹² Prior and concomitant medication cover any therapy including chemotherapy, radiotherapy and surgery or medication received in past or ongoing treatment.
- ¹³ All medications/therapies used to treat the tumor/symptoms under this study given to a patient ≤ 4 weeks after the last dose of study treatment must be recorded in the e-CRF. All patients will be followed for safety for 56 days from the last dose of study medication.
- ¹⁴ The safety follow-up has to be performed 56 ± 3 days after the patient received the last pasireotide LAR dose. For patients continuing into the extension study this visit will not be performed after the end of the main study but 56 ± 3 days after the patient has finished extension study.
- ¹⁵ ECG will be performed prior to the drug administration. In Visit 3 (Day 20) and Visit 6 (Day 76), ECG will be done independent of drug administration.
- 16 The window to perform MRI and gallbladder US should be no more than 7 days before the scheduled visit.
- ¹⁷ If patient will not be assigned for Extension Phase, follow-up visit will be Visit 11.

⁶ Serum pregnancy test will be performed in the final follow-up visit if patient report menstrual delay or as per physician discretion.

⁷ Blood and urine to be collected prior to study drug administration. Pts should be fasting for 12 hours.

⁸ Hematology and Coagulation include: Hemoglobin, hematocrit (HCT), WBC count with differential, RBC Count with differential and platelet count; PT and APTT.

 $^{^9}$ Complete biochemistry includes: total cholesterol, low density lipoprotein (LDL) cholesterol, high-density lipoprotein (HDL) cholesterol, triglycerides, calcium, phosphorus, chloride, sodium, potassium, inorganic phosphorus, creatinine, urea/BUN, uric acid, CPK, LDH, alkaline phosphatase, δ -GT, total protein, albumin, SGOT, SGPT, total bilirubin. If the total bilirubin concentration is increased above 2.0 times the upper normal limit, total bilirubin should be differentiated into the direct and indirect reacting bilirubin at visits.

Table A 2: Visit Schedule and assessments for extension study

Table A 2: Visit Schedule a	iiiu asses	3111611	13 101 6	EXCEIN	וטוו אנ	uuy															
Visit	10 ¹	11	12	402	13	14	15	16	17	18	19	20	21	22	23	24	25	26	27	28 TDE	29 FU ⁹
Week	24	28	32	35	36	40	44	48	52	56	60	64	68	72	76	80	84	88	92	96	Last dose + 8 weeks
Day	168	196	224	244	252	280	308	336	364	392	420	448	476	504	532	560	588	616	644	672	700
Injection	7	8	9		10	11	12	13	14	15	16	17	18	19	20	21	22	23	24		
Adverse events (D)	X	Х	Х	Х	Х	Х	Х	Х	Х	Х	Х	Х	Х	Х	Х	Х	Х	Х	Х	Х	х
Current medical conditions (D)	Х				Х			Х			Х			Х			Х			Х	х
Vital signs (D)	X				Х			Х			Х			Х			Х			Х	х
Physical exam (S)	Х				Х			Х			Х			Х			Х			Х	х
Weight (D)	Х				Х			Х			Х			Х			Х			Х	х
MRI / sella turcica	Х							Х						Х						Х	
Alpha subunit ²	Х							Х						Х						Х	
ECG (D)	Х				х			Х			Х			Х			Х			х	
Gallbladder ultrasound (D)	Х							Х												Х	
ECOG Performance status (D)	Х				Х			Х			Х			Х			Х			Х	х
Symptom assessment/ Disease related symptoms (D)	Х				Х			Х			Х			Х			Х			Х	
Serum pregnancy test ^{2,10}	Х							Х						Х						Х	
Hematology (D)	Х							Х						Х						Х	
Coagulation parameter PT (D)	XE	ХК	ХК	х	ХК	XK				Х	Х	Х	Х	Х	Х	Х	Х	Х	Х	Х	х
Coagulation parameter APTT (D)	XE					Х				Х	Х	Х	Х	Х	Х	Х	Х	Х	Х	Х	
Urinalysis ² (D)	Х							Х						Х						Х	

Fasting blood glucose and insulin ²	Х							Х						Х						Х	
HbA1c ²	х							Х						Х						Х	
Biochemestry ^{2,4}	Х							Х						Х						Х	
LFTs (ALT, AST, total bilirubin, albumin, ALP, γ-GT) (D)	Х			Х				Х						х						Х	
Hormonal evaluation ^{2,5} (D)	х							Х						Х						Х	
Visual field evaluation ⁶	Х							Х						Х						Х	
Vitamin B12, folic acid ²	Х							Х												Х	
Pariseotide LAR Admin ⁷ (D)	Х	Х	Х		Х	Х	Х	Х	Х	Х	Х	Х	Х	Х	Х	Х	Х	Х	Х		
Prior/Concomitant Meds ⁸ (D)	Х	Х	Х	Х	Х	Х	Х	Х	Х	Х	Х	Х	Х	Х	Х	Х	Х	Х	Х		
Study completition ⁹ (D)																					Х

¹ Patients will be invited to participate in the extension phase, according to the opinion of the treating physician, if they are benefiting from treatment with pasireotide LAR

² Blood and urine to be collected prior to study drug administration. Patients should be fasting for 12 hours.

³ Hematology and coagulation include: hemoglobin, hematocrit (Hct), WBC count with differential, RBC count with differential and platelet count, PT, and APTT.

⁴ Complete biochemistry includes: total bilirubin, total cholesterol, LDL, HDL, triglycerides, creatinine, urea, uric acid, δ -GT, total protein, albumin, AST, ALT, CPK, LDH alkaline phosphatase, sodium, potassium, inorganic phosphorus, and calcium chloride. If the total bilirubin concentration is increased above 2.0 times the upper normal limit, total bilirubin should be differentiated into the direct and indirect reacting bilirubin.

⁵ Hormonal evaluation (serum)—pituitary disease assessments: testosterone (for male), estradiol (for female), prolactin, free T4, TSH, LH, FSH, GH, IGF-1, cortisol, ACTH.

⁶ Assess with standard automated perimetry (SAP). It is suggested Humphrey Field Analyzer. The window to perform SAP should be no more than 7 days before the scheduled visit.

⁷ Patients will continue to receive pasireotide LAR i.m. every 28 (± 3) days. The drug administration will be performed by a health care professional in the site. The last dose administration is in Week 92 (Visit 27).

⁸ All medications/therapies used to treat the tumor/symptoms under this study given to a patient ≤ 4 weeks after the last dose of study treatment must be recorded in the eCRF. All patients will be followed for safety for 56 ± 3 days days from the last dose of study medication.

⁹ The safety follow-up visit (Visit 29) has to be performed 56 ± 3 days after the patient received the last pasireotide LAR dose.

¹⁰ Serum pregnancy test will be performed in the final follow-up visit if patient report menstrual delay or as per physician discretion

5 Statistical methods and data analysis

The following sections describe the analyses to be conducted.

For the Core Period of the study, efficacy and safety analyses will be conducted on the data collected by the time when all the enrolled patients have completed their EOS Visit. All the formal safety follow-up data of those patients who did not enter the extension study will also be included in the core study safety analyses. A final analysis will be completed when all the patients in the Extension complete their last visit and will be reported in either an additional clinical study report or in an addendum to the core study report.

Other additional data prior to the end of the Core Phase of the trial will be analyzed and then summarized in an additional report of clinical study or in a major study report.

Novartis or designated CRO will analyze all data using the SAS System for data analysis 9.4 . Any data analyses carried out independently by an investigator should be submitted to Novartis before publication or presentation.

The data from all centers participating in the trial will be combined, so that an adequate number of patients will be available for analysis. The statistical analysis methods described in this section will focus on the analysis of the data in the core study. Similar methods will be applied to the analyses in the Extension Phase as appropriate.

5.1 Populations for analysis

Full analysis set (FAS): consists of all patients who successfully completed the screening and have received at least one dose of study medication. FAS will be the primary set for all efficacy analyses.

Safety analysis set: consists of all patients who received at least one dose of study drug and had at least one post-baseline safety assessment.

Note the statement that a patient had no AEs (on the Adverse Event e-CRF) constitutes a safety assessment. The safety set will be used for all safety analyses.

The analyzes presented in this section represent the analyzes that will be used for the Core Phase of the trial. A final analysis will be performed when all patients of Extension Phase completed their last visit and will be reported or as additional clinical study report or as an addendum to the Core Phase of the trial report.

5.2 PATIENT DEMOGRAPHICS/OTHER BASELINE CHARACTERISTICS

Demographic and other baseline data including disease characteristics (e.g., age, sex, and race) will be summarized descriptively based on FAS. Categorical data will be presented as frequencies and percentages. For continuous data, mean, standard deviation, median, minimum, and maximum will be presented.

5.3 TREATMENTS (STUDY DRUG, CONCOMITANT THERAPIES, COMPLIANCE)

The duration of exposure to the study drug, number of patients with dose adjustment (i.e., interruptions, dose changes) and dose intensity will be summarized based on FAS for core and extension period of the study.

Concomitant medications and significant non-drug therapies prior to and after the start of the study drug will be summarized by preferred terms according to the ATC class of the WHO Drug Reference List.

5.4 PRIMARY OBJECTIVE

The primary objective is to assess the efficacy of pasireotide LAR in NFPA based on tumor volume reduction.

5.4.1 Variable

The primary efficacy variable is the proportion of patients with NFPA who achieve tumor volume reduction of at least 20% after Week 24 of treatment with pasireotide LAR.

5.4.2 Statistical Analysis

Proportion of patients with at least 20% of reduction in tumor volume will be summarized in terms of incidence rates and exact 90% confidence interval at end of core period of the study for FAS population (Week 24).

5.4.3 Handling of missing values/censoring/discontinuations

A patient whose tumor volume assessment at baseline (Visit 1) is missing will not be considered for the efficacy assessments. Only those patients will be considered for analysis for which baseline and at least one post baseline records are reflecting non missing values. All the analysis will be performed with as observed data i.e. the primary analysis (Week 24) will be based on only patients that have both baseline and Week 24 tumor volume assessment.

The analysis of the primary endpoint will be based on observed cases since the patients population is naive (including not having any surgery) and it is expected that 24 weeks of treatment is needed before meaningful effect are assessed.

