## 6.4.4 Discontinuation of the study drug

Patients experiencing unacceptable toxicity (grade  $\geq 3$  AE, including grade  $\geq 3$  changes in laboratory values) that the investigator considers as directly ascribable to the study drugs must have their doses decreased (Section 6.4.2) or be withdrawn from the study.

- Patients who permanently discontinue the study drug between Visit 2 and Visit 9 (inclusive) must be scheduled for the End of (Main) Study Visit (Visit 10) 28 ± 3 days after administration of the last dose of the study medication, when all evaluations listed will be performed. The Safety Follow-up Visit (Visit 11) will be performed approximately 56 ± 3 days after administration of the last dose of study medication.
- Patients who permanently discontinue the study drug in the Extension Phase must be scheduled for the End of (Extension) Study Visit 28 ± 3 days after administration of the last dose of the study medication, when all evaluations listed will be performed. The safety follow-up visit for the extension phase will be performed approximately 56 ± 3 days after administration of the last dose of the study medicaiton.

Patients who discontinue the study drug must be considered as withdrawn from the study after the EOS / Safety Follow-up evaluations are performed or when it's evident that the patient will not return for the EOS evaluations.

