#### 10.4.2 Statistical analysis

The proportion of patients with a decrease of at least 20% in tumor volume will be summarized in terms of incidence rates and the exact 90% confidence interval at the end of the main study for the FAS population (week 24).

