## 10.4.3 Control of missing values / censoring / discontinuations

A patient whose tumor volume evaluation at the beginning of the study (Screening Period, baseline data) is missing will not be considered for efficacy evaluations. Only patients with baseline evaluation and at least one later evaluation will be considered for statistical analysis. All analyses will be performed with the data observed, i.e. the primary analysis (Week 24) will only be based on data from patients with both baseline and Week 24 tumor volume evaluation.

The primary endpoint analyses will be based on the cases seen, as the population is treatmentnaïve (also not having undergone surgery), and 24 weeks of treatment are expected to be necessary before a significant effect is evaluated.

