5.4.4 Supportive analyses

A sensitivity analysis will be performed on primary efficacy endpoint after imputing the week 24 missing values by last observed carried forward (LOCF) technique, for patients having baseline and at least one post baseline value.

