Total (n=xx) HbA1c performed, n (%) Yes No Total HbA1c (%) Ν Mean Median Standard Deviation Minimum Maximum Normal Abnormal Clinically significant Non-clinically significant HbA1c ≤7% Yes No Total Fasting blood insulin (ulU/mL), n (%) Yes No Total Fasting blood insulin (ulU/mL) Mean Median **Standard Deviation** Minimum Maximum Normal Abnormal Clinically significant Non-clinically significant Fasting blood glucose (mg/dL), n (%) Yes No Total Fasting blood glucose (mg/dL) Mean Median Standard Deviation Minimum Maximum Normal Abnormal Clinically significant Non-clinically significant

Table 6 – Treatment – FAS population

	Tota (n=x															
		/2		V4		V5		V7		V8		V9		V10		ore nase
Study medication																
administered, n																
(%)																
Yes															-	-
No															-	-
Total															-	-
Dose, n (%) 60 mg															_	_
40 mg Total															-	-
Dose																
adjustment, n (%)																
Yes																
	-	-	-	-	-	-	-	-	-	-	-	-	-	-		
No Total	-	-	-	-	-	-	-	-	-	-	-	-	-	-		
Exposure																
(days) ^{a)}																
N	-	-	-	-	-	-	-	-	-	-	-	-	-	-		
Mean	-	-	-	-	-	-	-	-	-	-	-	-	_	-		
Median	-	-	-	-	-	-	-	-	-	-	-	-	_	-		
Standard	-	-	-	-	-	-	-	-	-	-	-	-	-	-		
Minimum	-	-	-	-	-	-	_	-	_	-	_	-	_	-		
Maximum	-	-	-	-	-	-	-	-	-	-	-	-	-	-		
Mean																
administration dose (mg)b)																
N	_	-	_	_	_	_	_	_	_	_	_	_	_	_		
Mean	-	-	-	-	-	-	-	-	-	-	-	-	-	-		
Median	-	-	-	-	-	-	-	-	-	-	-	-	-	-		
Standard	-	-	-	-	-	-	-	-	-	-	-	-	-	-		
Minimum	_	_	_	-	_	-	_	_	_	-	_	_	_	-		
Maximum	-	-	-	-	-	-	-	-	-	-	-	-	-	-		
Dose reduction																
before tumor volume																
reduction of at																
least 20%																
No																
Total																

a) The difference between the last administration and the first administration, in days.

b) Cumulative dose (total dose administered) divided by number administrations.

Table 7 – Magnetic resonance imaging – FAS population

	Total (n=xx)						
	V1	V4	95%CI	V7	95%CI	V10	95%CI
Volume (cm³)							
N			-		-		-
Mean			-		-		-
Median			-		-		-
Standard			-		_		_
Minimum			_		_		_
Maximum							
Tumor is not			_		_		_
Missing values			-		-		-
Volume change ^{a)}							
(cm³)							
N	-						
Mean	-						
Median	-						
Standard	-						
Minimum	-						
Maximum	-						
Percentage							
change in							
volume ^{a)} (%)							
N	-						
Mean	_						
Median	_						
Standard	_						
Minimum	_						
Maximum	-						

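### The primary response rate is labelled FAS but is an observed-case rate, and no planned analysis counts a missing Week 24 volume as non-response

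*SAP*

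**What the plan says.** SAP 5.1 defines the FAS as every patient who passed screening and was dosed at least once. No scan is required. It adds that "FAS will be the primary set for all efficacy analyses". SAP 5.4.2 sets the response proportion and its exact 90% interval "at end of core period of the study for FAS population (Week 24", and protocol 10.4.2 does the same "at the end of the main study for the FAS population (week 24". The output shell is headed "Table 7 – Magnetic resonance imaging – FAS population".

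The missing-data sections use a narrower denominator. SAP 5.4.3 states that "the primary analysis (Week 24) will be based on only patients that have both baseline and Week 24 tumor volume assessment". Protocol 10.4.3 says that this analysis "will only be based on data from patients with both baseline and Week 24 tumor volume evaluation". Both give a reason: the patients are treatment-naive, and about 24 weeks of treatment are thought necessary before an effect can be judged.

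The only sensitivity analysis in the SAP (5.4.4) is LOCF, "for patients having baseline and at least one post baseline value". The protocol synopsis also mentions repeating the primary analysis in a PPS population.

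On early stopping, protocol 6.4.4 says that patients who permanently stop the drug between Visits 2 and 9 "must be scheduled for the End of (Main) Study Visit (Visit 10) 28 ± 3 days after administration of the last dose", with all listed evaluations done. Protocol Table 7-1 includes an MRI at Visit 10 and labels that visit Week 24. SAP Table 7 heads the corresponding column only V10.

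**The concern.** The main efficacy result is a single proportion with an exact interval, read against the 10% response level that SAP 5.6 calls clinically meaningful. If the table says FAS but the denominator leaves out dosed patients, the number is not what its label says.

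The omitted patients need not be a random subset. Protocol 6.4.5.1 lists confirmed tumour growth above 20%, confirmed vision loss and adverse events among the reasons for withdrawal. Patients who leave for these reasons can drop out of the denominator.

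The planned alternatives do not fill the gap:

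- LOCF normally returns a confirmed-growth patient as a non-responder. But it omits dosed patients with no post-baseline scan, and it can carry a Week 4 or Week 12 response forward to Week 24.
- The PPS repeat does not impute non-response.

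A second, conditional issue is the V10 label. A scan taken at an early stopper's Visit 10 could be counted as Week 24 if the table is programmed by visit label.

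**Working it through.** **Inputs.** SAP 5.6 gives 23 enrolled, 19 evaluable, 20% dropout, and intervals for 2 to 6 responders out of 19. I assume that all 23 are dosed and in the FAS, that 23 − 19 = 4 lack a Week 24 volume, and that all observed responders are among the 19.

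**Reproducing the plan.** P(X ≥ 2 | n = 19, p = 0.10) = 1 − 0.9^19 − 19 × 0.1 × 0.9^18 = 1 − 0.135 − 0.285 = 0.580, which matches the stated 58%. The exact (Clopper-Pearson) limits are: lower = the α/2 quantile of Beta(r, n − r + 1); upper = the 1 − α/2 quantile of Beta(r + 1, n − r). For 2/19 at 90% they are 1.9% and 29.6%, as in SAP Table A 4. The rows for 3 to 6 responders also match.

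**Observed-case against FAS with missing as non-response.** The gap is r/19 − r/23 = 4r/437.

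| Responders | r/19 (90% CI) | r/23 (90% CI) | Gap, points | 95% lower limits, /19 and /23 |
|---|---|---|---|---|
| 2 | 10.5% (1.9–29.6) | 8.7% (1.6–24.9) | 1.8 | 1.3, 1.1 |
| 3 | 15.8% (4.4–35.9) | 13.0% (3.7–30.4) | 2.7 | 3.4, 2.8 |
| 4 | 21.1% (7.5–41.9) | 17.4% (6.2–35.5) | 3.7 | 6.1, 5.0 |
| 5 | 26.3% (11.0–47.6) | 21.7% (9.0–40.4) | 4.6 | 9.1, 7.5 |
| 6 | 31.6% (14.7–53.0) | 26.1% (12.0–45.1) | 5.5 | 12.6, 10.2 |

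**Varying the number missing.** With 2 responders and 0, 2, 4, 6 or 8 missing (an assumed range), the observed-case rate is 8.7%, 9.5%, 10.5%, 11.8% or 13.3%. The FAS rate stays at 8.7%.

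**Direction.** With 2 of 19 responding, the rate over all 23 would be 2/23 = 8.7% if none of the 4 missing patients would have responded, 3/23 = 13.0% if one would, and 6/23 = 26.1% if all would. If each had a 10% chance (an assumption), at least one would respond with probability 1 − 0.9^4 = 0.34.

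**Early-stop Visit 10 scans.** A last dose at Visit 2, 4, 5, 7 or 8 (Day 0, 28, 56, 84 or 112) plus 28 days puts Visit 10 at nominal Day 28, 56, 84, 112 or 140, that is, Week 4 to Week 20. A patient last dosed at Visit 9 (Day 140) has had all six core injections and comes at nominal Day 168.

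**The case against.** The observed-case rule is stated openly in both documents, with a reason, and the sample size is built on 19 evaluable patients. The denominator is therefore consistent with the design. That stands. The fault lies in the label and the missing companion analysis; nothing is concealed.

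A reader might infer that the all-patient figure is unavailable. It is not. SAP Table 1 gives the FAS size, and SAP Table 7 gives responder counts and missing values by visit, so the proportion is one division away. What is absent is a labelled row with its interval.

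A reader might also take the table above to show that the denominator decides whether 10% is excluded. That happens only with 5 responders, and only at the 90% level of SAP 5.4.2 (11.0% against 9.0%). SAP Table 7 has 95% interval columns, and SAP section 7 replaces 90% by 95%. At 95% both lower limits are below 10% with 5 responders and both are above it with 6. The documents treat 10% as a level of relevance and attach no decision rule to it.

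Finally, a reader might infer that early stoppers' scans will be counted as Week 24. An ordinary reading of SAP 5.4.3 excludes them. The harm arises only if the table is built from the V10 label, and in that case those patients would not be missing and the gap between 19 and 23 would shrink. LOCF should also cover most early stoppers, since they are scheduled for a Visit 10 MRI.

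**Conclusion.** The primary rate is mislabelled: it is an observed-case rate presented as an FAS rate, and no planned analysis counts missing as non-response. With 23 in the FAS and 19 observed, the difference runs from 1.8 points at 2 responders to 5.5 points at 6. It is small beside the width of the intervals. With 2 responders the point estimate moves from just above 10% to below it, but both intervals contain 10%.

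The documents do not support a claim that the observed-case rate must be too high. Some missing patients may have left for neutral reasons or might have responded, so the direction of bias is uncertain. The ambiguity over Visit 10 is real but secondary. The study is a proof of concept with no power target, so what is affected is how one estimate is reported and read; no test is invalidated. The correction is worth making because it costs almost nothing.

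**What to change.** In SAP 5.4.2 and Table 7, report as the FAS result the number of Week 24 responders divided by all FAS patients, counting a missing volume as non-response, with an exact CI. Relabel the present analysis observed-case, and keep it and LOCF alongside.

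Add one sentence before analysis: a Visit 10 scan from a patient who stopped before the sixth core injection (last dose at Visit 8 or earlier) is not a Week 24 value and enters LOCF only.

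Do not define this by a fixed calendar window. Day 168 ± 3, with the MRI up to 7 days before, gives Day 158 to 171. But a patient last dosed at Visit 9 can have Visit 10 between Day 137 + 25 = 162 and Day 143 + 31 = 174. If 28 ± 3 days is read as the interval between visits, Visit 10 can fall anywhere from 6 × 25 = Day 150 to 6 × 31 = Day 186. On that reading a Visit 8 stopper's visit can reach 5 × 31 = Day 155 and the scan Day 162 (protocol section 4 allows 7 days), inside the window. A fixed window could therefore turn patients with all six injections and a real scan into non-responders, and still admit some early stoppers.

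The cost is a wording change, one sentence and one extra table row, with no new data. The downside is that the FAS figure will be slightly less favourable, and it is conservative if some dropouts were unrelated to efficacy.
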